3 ANALYSIS AND OUTCOMES

3.1 OUTCOME

Stimulant use will be assessed by the ASI, clinical history, and the UDS starting at intake. The MINI module completed by the treating psychiatrist will determine stimulant use disorder. A stimulant use disorder is necessary to be eligible to participate.

Primary outcome will be the number of relapse days between week 2 and 12. We assume relative small number of relapses, but stimulant use (specifically crystal meth use) is the biggest concern for relapse in the centre and individual relapses occur most commonly with stimulants.

We further measure craving and implicit association as potential mediators of relapse and they may help explain individuals' tendencies to relapse to stimulant use.

Week:	Baseline	1	2	3	4	5	6	7	8	9	10	11	12
Intervention:													
Sessions		***	***	**	**	*	*	*	*				
Outcome:													
UDS	^			^	^	^	^	^	^	^	^	^	^
Craving Questionnaire	X				X				X				X
Behaviour Association Questionnaire	BA				BA				BA				BA

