1.2 HYPOTHESIS

1.2.1 The intervention will be easy to integrate into the existing program.

1.2.2 Participation in the experimental (stimulant-avoidance) condition will reduce craving (as assessed by the stimulant craving questionnaire brief version), show reduction in an automatic association of activities with stimulant use and stimulant relapses (as assessed by behaviour association questionnaires) and have reduced relapses as assessed by urine drug screens in 12 weeks following initiation of the intervention.

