2.2 MEASURES

The information and consent form will include information regarding access to clinical documentation to complete the characterization of individuals including socio-demographic data, clinical diagnoses, use history, medication, and cognitive characterization. All participant clients are well characterized within the treatment program at BCMHA. We will access data from the treatment provider, complement missing data and add assessments, such as a cognitive assessment component (including working memory, motor inhibition, and spatial memory). Access to clinical information will be limited to the client's current treatment program. We are thus in a position to identify factors (socio-demographics, mental disorders, substance use disorders, cognitive characteristics, smoking history, etc.) associated with treatment outcome.

During the appointment, participants will complete a battery of questionnaires as listed in the study protocol. Participants will complete questionnaires using a tablet, unless they request a paper survey. The Qualtrics system contracted through UBC and approved by UBC for ethical privacy and data storage practices, will be used for completing questionnaires and chart reviews. This will reduce the need for double data entry, reducing the overall cost and assuring data quality.

Outcome measures are:

- *Craving as assessed by the stimulant craving questionnaire-brief (Paliwal 2008).*
- *Behavioural association as assessed by the behaviour association scale, which measures the degree to which substance use is associated with a number of different situations (Krank 2010).*
- *Relapse to use as identified by self-report and regular urine drug screen.*

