2.4 DURATION

A CEASAR session will last 15 minutes. Study participants will take part in three sessions per week in the first two weeks, then two sessions per week in the following 2 weeks, and then one session per week thereafter. Each patient will participate in a total of 14 sessions over a period of 8 weeks. The outcome assessment will cover 12 weeks after the initiation of the intervention (4 weeks after the last CEASAR session). While a six month follow up would be preferred, given the pilot character of the study and the average length of stay of 4 months, we decided to focus on the three-month period as a pilot.

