2.6. COMPENSATION

Participants will be compensated with \$10 for every assessment (lasting less than one hour) and \$5 for participation in the intervention (lasting 15 min) independent of study completion, in the form of a gift card or voucher. Thus, the client can accumulate an upper limit of \$110. As clients will be compensated using the contingency management program at BCMHA, funding will support this program, allowing the client to receive “rewards” of his or her choice, but not monetary compensation. If preferred by the participant, we will alternatively compensate in the

Computerized exercise to alter stimulant approach responses (CEASAR)
form of a gift card.

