3.2 STATISTICAL ANALYSIS

Relapses: Cumulative relapses will be compared using simple t-tests. Further analysis using linear regression models will account for potential baseline differences (due to randomization). The clinical urine drug screens will provide the basis for calculating relapses.

Craving: Stimulant craving reduction (baseline versus week 12) will be compared to the placebo group, as assessed by the Stimulant Craving Questionnaire-Brief (SCQ-B) (Paliwal 2008). Statistical analysis will be similar to the primary outcome with t-test and linear regression models.

Behaviour Association scale: The scale has four dimensions, which will be analyzed separately (see above).

The study will have to be approved by the ethics committee and the PHSA research board before initiation. It will be registered with Clinical Trial at NIH.

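### The primary outcome counts relapse days, but it is to be calculated from weekly urine screens, which do not determine days, and no conversion rule is given

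*Combined protocol and SAP*

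**What the plan says.** - **Outcome (section 3.1).** "Primary outcome will be the number of relapse days between week 2 and 12".
- **Analysis (section 3.2).** The quantity compared has another name: "Cumulative relapses will be compared using simple t-tests". Its source is stated: "The clinical urine drug screens will provide the basis for calculating relapses".
- **Schedule (table in section 3.1).** The UDS row has one mark at baseline, none in weeks 1 and 2, and one in each of weeks 3 to 12.
- **Other sources.** Section 2.2 lists the outcome as "Relapse to use as identified by self-report and regular urine drug screen". Section 3.1 adds: "Stimulant use will be assessed by the ASI, clinical history, and the UDS starting at intake".
- **Hypothesis (section 1.2.2).** It expects "reduced relapses as assessed by urine drug screens in 12 weeks following initiation of the intervention", a looser window than the UDS row.

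The document does not define a relapse or turn a positive screen into days. It also does not say how a missed screen counts or name the analysis population.

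**The concern.** A day of use, a relapse episode and a positive screen are three different quantities. The plan names the first as the primary outcome and analyses something called by the second name, using data that supply only the third. Two analysts could report different primary results for the same participants: one sums positive screens, the other tries to build days with help from self-report. Nothing in the plan prevents that choice from being made after the data are seen. The pilot tests efficacy on this outcome and is meant to support a full trial (section 3.3), so an outcome with no fixed unit would be a weak basis for it.

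A second, smaller gap follows from the first. If relapses are simply summed over screens, a screen that was never obtained adds zero, as a negative one does. Section 2.5 expects some non-completion and section 2.1.1 allows exclusion during an acute crisis, so some screens will probably be missing.

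**Working it through.** The plan has no figure of its own to reproduce here: it gives no relapse rate, and the sample size is a pilot convention. The check is whether the scheduled data fix the stated outcome.

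**1. How many screens.** In the same table the session marks are 3 + 3 + 2 + 2 + 1 + 1 + 1 + 1 = 14. Section 2.4 says: "Each patient will participate in a total of 14 sessions over a period of 8 weeks". One mark is therefore one occurrence in the session row. Read the same way, the UDS row gives 10 screens after baseline, covering 10 × 7 = 70 days.

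**2. Which day counts fit a screen result.** Assume a screen on the last day of each week that detects use in the previous W days, with W at most 7. The documents give no W, so it is varied. With k positives out of 10, the number of use days lies between k and Wk + 10(7 − W).

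| Positives k | W = 7 | W = 3 | W = 1 |
|---|---|---|---|
| 0 | 0 | 0 to 40 | 0 to 60 |
| 1 | 1 to 7 | 1 to 43 | 1 to 61 |
| 3 | 3 to 21 | 3 to 49 | 3 to 63 |
| 10 | 10 to 70 | 10 to 70 | 10 to 70 |

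These are logical limits, not expected values. With W above 7 the lower limit fails too, because one use could turn two screens positive.

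**3. The reverse direction.** Six use days were placed at random in the 70 days, in 20,000 simulated patterns. With W = 7, scattered days give a mean of 4.8 positive screens and a single six-day run gives 1.7. With W = 3 the means are 2.4 and 1.1. The count depends on the pattern of use as well as on the number of days.

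**4. Whether another source supplies days.** No row of the schedule is a day-level record. The payment cap in section 2.6 ("the client can accumulate an upper limit of" $110) equals 14 × $5 + 4 × $10. That fits 14 sessions and four assessments (baseline, weeks 4, 8 and 12). Use could be asked about at those assessments, but no day-by-day recall is specified.

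**5. Missed screens under a plain sum (illustration only).** Assume 35 per arm and 10 leavers (70 budgeted maximum minus 60 minimum completers) split 3/7. Assume also equal true positivity p in both arms, and s screens obtained per leaver. The mean count in an arm with n leavers is p × [10(35 − n) + ns]/35.

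| s | n = 3 | n = 7 | Difference |
|---|---|---|---|
| 1 | 9.229p | 8.2p | 11.1% lower |
| 3 | 9.4p | 8.6p | 8.5% lower |
| 5 | 9.571p | 9.0p | 6.0% lower |
| 7 | 9.743p | 9.4p | 3.5% lower |

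With equal leaving risk, a split of 3/7 or more uneven in either direction has hypergeometric probability 0.306.

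To set the 8.5% against noise, assume Poisson-like counts. At p = 0.1 the means are 0.94 and 0.86, a gap of 0.08. The standard error is √[(0.94 + 0.86)/35] = 0.227, so the gap is about 0.35 standard errors. At p = 0.3 it is 0.24/√[(2.82 + 2.58)/35] = 0.61 standard errors.

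**The case against.** Several points on the other side stand and limit the claim.

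- **UDS already has priority.** A reader might infer that the sources are wholly unranked. The documents do not support that: section 3.2 makes UDS the basis, and section 1.2.2 names UDS alone. The sentence on the ASI and clinical history refers to intake and sits beside the eligibility sentences, so it can be read as characterising participants. What remains open is the role of self-report, which section 2.2 lists jointly with UDS. Priority for UDS also supports a screen count, not a count of days.
- **Missed screens are not scored as negative by any stated rule.** A reader might infer that they are. The plan is silent, and scoring them as negative is only what a plain sum would do. Section 2.5 speaks of completers. If only completers were analysed, leavers would contribute no count and the illustration would not arise.
- **The treatment comparison is not shown to be biased.** A reader might take the seven-fold range or the 8.5% as an expected distortion. The range concerns one participant's days, and a count of positive screens can still be compared between randomised arms. The 8.5% rests on a chosen split with leavers kept in the analysis, and it is small beside sampling noise.
- **Weekly frequency is read from the table.** The text calls the screens only regular, and clinical screens might be more frequent. No such schedule is stated, however, and extra screens would make a sum depend on how often someone was tested.
- **The window is a minor point.** The period in section 3.1 can be read as starting after week 2, which matches the UDS row. Only section 1.2.2 is looser.

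That this is a pilot with a feasibility question lowers the stakes, but it does not make the stated outcome computable.

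**Conclusion.** The concern holds in this form: the primary outcome is stated in days, the screens scheduled to supply it do not determine days for any detection window examined, and no conversion rule exists. This is an inconsistency between sections 3.1 and 3.2, not merely missing detail, and it should be corrected before outcome data are examined. Its size is the width of what the data leave open, which is 3 to 21 days for three positives under the assumption most favourable to the plan. That rests on reading the schedule as one screen a week. The missed-screen gap is real but secondary, and its effect is not established: 3.5% to 11.1% in the illustrations, none if only completers are analysed.

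**What to change.** In sections 3.1 and 3.2, replace both the day count and the cumulative relapses with one outcome: *the proportion of obtained weekly UDS in weeks 3 to 12 that are stimulant-positive, with at most one result per study week*. Say in advance which result is used if a week has more than one, for example the first, so that the value does not depend on testing frequency. A 0 to 10 count of positive weeks is an acceptable alternative only if a missed-screen rule is stated with it. Keeping days would need a day-level record, a conversion rule and an order of sources, none of which the plan has.

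Then:
- keep the planned t-test and linear regression;
- align source and window in sections 1.2.2 and 2.2, and state that self-report does not enter the primary outcome;
- report by arm the number of missed screens and of participants with no screen, who have no primary value.

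An analysis counting missed screens as positive may be added, but only as a bound with its artefact stated. In the 3/7 illustration with three screens per leaver, its value is [10(35 − n)p + n(3p + 7)]/350. Equal true positivity of 10% then appears as 0.154 against 0.226, and 30% as 0.342 against 0.398. At 10% that is a larger relative gap (0.226/0.154, or 47% higher) than the 8.5% under a plain sum.

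**Cost.** Wording in four sections and a short table, with no new data, visits or staff. The outcome is coarser than days, weeks 1 and 2 are not covered, and participants with few screens give noisy values. The proportion is unbiased only if missed screens are unrelated to use, and the plan should say so.

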3.2 STATISTICAL ANALYSIS

Relapses: Cumulative relapses will be compared using simple t-tests. Further analysis using linear regression models will account for potential baseline differences (due to randomization). The clinical urine drug screens will provide the basis for calculating relapses.

Craving: Stimulant craving reduction (baseline versus week 12) will be compared to the placebo group, as assessed by the Stimulant Craving Questionnaire-Brief (SCQ-B) (Paliwal 2008). Statistical analysis will be similar to the primary outcome with t-test and linear regression models.

Behaviour Association scale: The scale has four dimensions, which will be analyzed separately (see above).

The study will have to be approved by the ethics committee and the PHSA research board before initiation. It will be registered with Clinical Trial at NIH.

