2.1.1 Patients

The inclusion criteria for participants are:

- Adult: Must be 19 years or older
- "Current" stimulant use disorder (cocaine, crack cocaine, amphetamine, methamphetamine, crystal meth), active before intake at BCMHA (assessed by MINI)
- Competent to consent: Must understand the consent form and give informed consent
- Proficient in English

This study will enrol both male and female subjects, and requires proficiency to read and write in English in order to understand the consent form. Additionally, patients must have been diagnosed with a stimulant use disorder (mainly cocaine use disorder, methamphetamine use disorder). Patients will be recruited at the centre using flyers and through active recruitment of clinic clients by interviewers. Once a client has indicated interest in the study, an interviewer will provide the potential participant with the consent form, review the consent form and if possible, gain informed consent from all participants. Participants will be given enough time to decide whether or not they wish to participate. They may decide to participate in the study at any time,

Computerized exercise to alter stimulant approach responses (CEASAR)

given that the study is still being conducted and that the participants will still be at the BCMHA for 12 weeks once they agree to begin the study.

Interested clients will be screened during the consent process for eligibility. In addition, participants may be excluded during the study in the case of acute crises not allowing them to regularly participate. This will be determined by the treating psychiatrist, and could arise from situations such as psychotic decompensation, an acute depressive episode, or a manic or hypomanic episode.

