2.5 SAMPLE SIZE

For the pilot study we plan to recruit a minimum of 60 participants to complete 12 weeks of the pilot study. A recent review on pilot sample data suggested a sample size of 10-40 per group (Herzog 2008)³; with 30 completers at each group, we will be on the upper end of the suggested sample size.

If we recruit 10 individuals every month, we will complete recruitment in approximately 6-8 months (depending on non-completion). The plan is to complete the study in approximately one year.

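### The primary relapse comparison uses raw totals and ignores how many urine screens each person gave, so early leaving that differs by arm or is related to relapse can distort it

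*Combined protocol and SAP*

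**What the plan says.** Section 3.1 defines the endpoint: "Primary outcome will be the number of relapse days between week 2 and 12". It adds "We assume relative small number of relapses" and gives no rate, mean or standard deviation. Section 3.2 names the data source, "The clinical urine drug screens will provide the basis for calculating relapses", and the test, "Cumulative relapses will be compared using simple t-tests". The regression that follows adjusts for baseline imbalance and has no term for time observed. The schedule in section 3.1 marks a baseline screen and then weekly screens in weeks 3 to 12, ten in all.

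On follow-up, section 2.1.1 says "participants may be excluded during the study in the case of acute crises not allowing them to regularly participate", as judged by the treating psychiatrist. Section 2.5 sets the size in completers ("we plan to recruit a minimum of 60 participants to complete 12 weeks of the pilot study", 30 per group) and lets the recruitment period vary with non-completion. The budget in section 5 allows at most 70 participants. No section gives an analysis population, a rule for missed screens or a rule for people who leave early.

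**The concern.** A total built from urine screens cannot exceed the number of positive screens collected. On the section 3.1 schedule, someone who leaves after week 4 has given two post-baseline screens and can score at most 2, while a completer can score up to 10. If leavers enter the t-test with their totals, screens never taken are treated as negative.

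If only completers are analysed, as the framing of section 2.5 might suggest, everyone has the same ten scheduled screens. The comparison is then between selected groups. Removal for psychotic, depressive or manic episodes could well be related to relapse, so that selection is not obviously harmless.

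Either way, the primary between-arm difference can mix relapse with length of observation or with who stays. It could suggest a benefit that is not there, or hide one that is. Section 3.3 intends the pilot to support a full trial, so a distorted estimate would carry forward.

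**Working it through.** **Inputs from the documents.** Ten post-baseline screens (3.1); 30 completers per group, 60 in total (2.5); at most 70 participants (5). The plan's sample size rests on a rule of thumb for pilots, so there is no power calculation to reproduce. The implied non-completion is 70 − 60 = 10, and 10/70 = 14.3%.

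**Assumptions, because the documents give none.** 35 randomised per arm, no true effect, leavers kept with their raw totals, and two-sided t-tests at 0.05. Two simulation models were used:
- *Count model:* mean 0.5, 1 or 2 underlying relapses per person, gamma heterogeneity with shape 0.5 or 1, and leaving time uniform over the window (leavers average about 4.5 screens).
- *Beta-binomial model:* positive rate per screen mainly 10-30%, between-person correlation 0.1-0.2, and leavers averaging about 5 screens.

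**Size of the mechanical shift.** If leaving is unrelated to relapse, the expected ratio of raw totals equals the ratio of mean screens obtained. With L leavers of 35 who average m screens, mean screens = [(35 − L) × 10 + L × m] / 35.

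| Leavers per arm | Mean screens, m = 4.5 | Ratio, m = 4.5 | Ratio, m = 5 |
|---|---|---|---|
| 5 v 5 | 9.21 v 9.21 | 1.00 | 1.00 |
| 7 v 3 | 8.90 v 9.53 | 0.93 | 9.00/9.57 = 0.94 |
| 10 v 0 | 8.43 v 10 | 0.84 | 8.57/10 = 0.86 |

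The simulated ratios agree with these.

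**Type I error of the raw-total t-test.**
- Nobody leaving: 4.2-5.1%.
- 7/3: 4.6-5.2% (count model); 5.0-5.7% (beta-binomial).
- 10/0: 6.3-9.5% (count model); about 5-14% across all runs, highest at the highest assumed positive rates.
- 15% v 40% leaving: at a 20% positive rate the mean totals are 1.85 v 1.60, and 1.60/1.85 = 0.86, a false reduction of about 14%. Error is about 5-13%. This pattern means 0.15 × 35 + 0.40 × 35 = 19.25 leavers and about 51 completers, short of 60.

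**Per-screen analysis in the same settings.** Rate ratio 0.99-1.01 in the count model. A t-test on positives divided by screens obtained has error of about 5% in the beta-binomial model.

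**Masking a real effect.** With a true rate ratio of 0.5, a control rate of 20%, and 40% of controls v 15% of the active arm leaving, power is 48% on raw totals v 66% per screen at correlation 0.1. At correlation 0.2 it is 37% v 54%.

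**Relapse-related leaving** (count model, mean 1, shape 0.5; the highest-risk clients leave; no true effect):

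| Split | Raw total | Per week observed | Completers only | Raw t-test error |
|---|---|---|---|---|
| 7 v 3 | 0.83 | 0.89 | 0.70 | 10.6% |
| 10 v 0 | 0.60 | 0.72 | 0.39 | 23.3% |

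The rate is the least biased of the three, but it is still biased. With 5 v 5 high-risk leavers the raw ratio stays at 1.01, although the t-test error was 8.6%.

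**The case against.** The strongest reply is that nothing in the documents predicts unequal leaving. Both arms do the same joystick task under a placebo design. Entry at any time might be read as a further source of unequal follow-up, but section 2.1.1 requires participants to have 12 weeks left at the centre, which is meant to equalise it. Similarly, "the average length of stay of 4 months" exceeds 12 weeks, and section 2.4 gives it as a reason for the three-month window. It is an average, so some stays may be shorter, but it is weak evidence. At the attrition the budget implies, a 7/3 split leaves the t-test close to nominal. The plan also never says that leavers keep truncated totals.

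All of this stands, and it limits the size of the problem. It does not remove it, because crisis exclusions and non-completion are in the plan and neither reading of who is analysed is protected.

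Two stronger readings should be set aside. A reader might infer that a sparse, skewed count makes the t-test invalid. With nobody leaving, its error was 4.2-5.1%, so sparseness alone is not the fault. A reader might also infer that reporting totals prevents planning of the full trial. It does not, because the same screens yield a rate and its overdispersion whichever test is used.

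**Conclusion.** The point holds in a conditional form. Section 3.2 takes no account of screens obtained and states no rule for leavers, so the primary comparison is exposed to bias if leaving differs by arm or is related to relapse. The documents do not show that a false treatment difference will occur.

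At the budget-implied 10 leavers of 70 and leaving unrelated to relapse, the false reduction is about 6% for a 7/3 split, with error near 5%. For the extreme 10/0 split it is about 14-16%, with error of about 5-14%. Larger distortions need relapse-related leaving or losses that would miss the plan's own minimum of 60 completers. All relapse rates, heterogeneity values and leaving patterns are assumptions.

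This should be fixed because it concerns the primary analysis and the remedy is cheap. It is not a fatal flaw.

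**What to change.** In section 3.2:

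1. Make the primary analysis stimulant-positive screens out of screens obtained, in all randomised participants with at least one post-baseline screen. Someone with no screen cannot enter a model with a log offset.
2. Fit a quasi-Poisson or negative binomial model with log(screens obtained) as offset and terms for arm and baseline UDS. Report the rate ratio with 95% CI. Take the p-value from permuting arm labels, because quasi-Poisson error ran at 4-6.5% at this size. The error near 5% shown above is for a t-test on per-screen proportions; the offset model with a permutation p-value was not itself simulated, so check it before finalising the text.
3. Report by arm the number with no post-baseline screen and the number of screens obtained.
4. The offset removes only the mechanical part of the bias. Add a sensitivity analysis for relapse-related leaving that includes all randomised participants, for example with missing screens counted as positive. Read it as a bound rather than an estimate.
5. Keep the raw-total t-test as a further sensitivity analysis.

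This needs no new visits, data or participants. The costs are a rate ratio that is slightly harder to explain than a mean difference, and a change in section 3.1 so that the outcome is stated as positive screens rather than relapse days.

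### Craving is collected at weeks 4, 8 and 12 but compared only at week 12, so the plan gives no end-of-training estimate and no use for the scores of participants who leave early

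*Combined protocol and SAP*

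**What the plan says.** All references are to the combined protocol and SAP.

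- **Collection.** In the schedule of section 3.1 (Outcome), the row "Craving Questionnaire" is marked at baseline and weeks 4, 8 and 12. The behaviour association row has the same four marks.
- **Training.** Section 2.4 (Duration): "Each patient will participate in a total of 14 sessions over a period of 8 weeks". On follow-up: "The outcome assessment will cover 12 weeks after the initiation of the intervention (4 weeks after the last CEASAR session").
- **Analysis of craving.** Section 3.2 (Statistical Analysis): "Craving: Stimulant craving reduction (baseline versus week 12) will be compared to the placebo group". On method: "Statistical analysis will be similar to the primary outcome with t-test and linear regression models".
- **Analysis of behaviour association.** Section 3.2 says that the four dimensions are analysed separately and points back to the text above. It names no visit.
- **Second role.** Section 3.1: "We further measure craving and implicit association as potential mediators of relapse". Section 3.2 contains no mediation model.
- **Numbers.** Section 2.5 (Sample Size): "we plan to recruit a minimum of 60 participants to complete 12 weeks of the pilot study". The same section allows for non-completion without giving a rate. Section 5 (Budget) provides for at most 70 participants.
- **Removal.** Section 2.1.1 (Patients) allows exclusion during the study for acute crises, as judged by the treating psychiatrist.

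The document gives no missing-data rule and defines no analysis population.

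**The concern.** Three post-baseline craving scores are planned and one is analysed. Two things are lost.

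First, the only planned contrast falls 4 weeks after the last session. If it shows no difference, the pilot cannot say whether craving never changed or whether it changed by the end of training and then returned. Section 3.3 says the pilot is to support a full trial, and the two explanations would lead to different designs for that trial.

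Second, a baseline-to-week-12 change needs a week-12 score. Someone who completes the week 4 and week 8 questionnaires and then leaves contributes nothing to the craving comparison, although the post-baseline scores are on file. Because section 2.1.1 allows removal for acute crises, those lost may differ from those who stay.

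**Working it through.** **1. Reproduce the plan's own figures.**
- Sessions (2.4 and the 3.1 schedule): 3×2 + 2×2 + 1×4 = 14. This agrees with the stated total. Of these, 6 + 4 = 10 fall in weeks 1–4.
- Payment cap (2.6): 14×$5 + 4×$10 = $110. This agrees with the stated limit and fits four paid assessments: baseline and weeks 4, 8 and 12.
- Gap from the last session to the last assessment: 12 − 8 = 4 weeks, as stated.

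**2. Set collection against analysis.**

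| Visit | Craving collected (3.1) | Used in a stated comparison (3.2) |
|---|---|---|
| Baseline | yes | yes |
| Week 4 | yes | no |
| Week 8 (training ends) | yes | no |
| Week 12 | yes | yes |

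Two of three post-baseline scores have no stated analysis. If the back-reference for the behaviour association scale imports the craving comparison, the same holds there. If it does not, the scale has no stated time point.

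**3. How many could lack a craving outcome.** The inputs are 70 (budget ceiling) and 60 (target completers): 70 − 60 = 10, and 10/70 = 14.3%. This combines a ceiling with a target and is not a stated dropout rate. As assumed alternatives, 25% or 30% dropout from 70 would leave 70×0.75 = 52.5 (about 52) or 70×0.70 = 49 participants with a week-12 change.

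**4. What the intermediate visits add.** None of the following assumptions is in the documents: SD 1, equal correlation ρ between all visits, 30 completers per arm, and a further 5 per arm leaving after week 8. Standard errors of the between-arm difference:
- Change score, completers: √[2(1−ρ)·2/30]
- Baseline-adjusted, completers: √[(1−ρ²)·2/30]
- Longitudinal model, all available visits: from the inverse of its information matrix
- Week 8, all 35 per arm: √[(1−ρ²)·2/35], which the longitudinal model reproduces

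| Estimate | ρ = 0.3 | ρ = 0.5 | ρ = 0.7 |
|---|---|---|---|
| Week 12, change score, completers | 0.306 | 0.258 | 0.200 |
| Week 12, baseline-adjusted, completers | 0.246 | 0.224 | 0.184 |
| Week 12, longitudinal model | 0.245 | 0.221 | 0.181 |
| Week 8, longitudinal model | 0.228 | 0.207 | 0.171 |

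Relative to baseline-adjusted completers, the longitudinal model lowers the week-12 standard error by 0.001/0.246 = 0.4%, 0.003/0.224 = 1.3% and 0.003/0.184 = 1.6%. Nearly all of the improvement over the change-score t-test comes from baseline adjustment. What the model adds is the week-8 row, which the plan does not estimate, and the use of early leavers' scores.

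**The case against.** The strongest defence is that week 12 is a sound choice. A single prespecified time point limits multiplicity, matches the 12-week outcome window, and asks whether an effect outlasts training. That stands: choosing week 12 is not an error, and the point concerns only what is left unused.

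A second defence is that weeks 4 and 8 serve the mediator role in section 3.1. They might, but section 3.2 states no mediation analysis, so on the text those scores are still unused.

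A third is that the plan does not tell anyone to drop early leavers; it is silent on missing data, for the primary outcome too. That is fair. The loss follows from defining the outcome as a baseline-to-week-12 change with no rule for a missing week-12 score.

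Some stronger readings are tempting but not supported:
- *The effect should peak at week 4 or 8 and fade.* The front-loaded schedule may suggest this, but no section predicts it. The background likens the training to learning to ride a bike, which if anything points to persistence. Fading is a possibility the plan cannot examine, not an expectation.
- *People who relapse leave.* Section 2.1.1 supports removal for acute crisis only.
- *Using all visits greatly sharpens the comparison.* Under equal correlations of 0.4 to 0.7, the average of the three visits has a standard error 0.72 to 0.78 of that for week 12 alone. That average is a different quantity from the week-12 effect, where the gain is about 0.4–1.6%.

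**Conclusion.** The concern holds in a limited form. Followed as written, section 3.2 leaves two of the three post-baseline craving scores without an analysis, gives no estimate at the end of training, and yields no craving change for anyone without a week-12 score. The number so affected is up to 10 of 70 if the budgeted maximum enrols and 60 complete; the true figure is unknown because no dropout rate is given. How many of them could be recovered depends on when they leave: only those who reach week 4 have a post-baseline score. None of this makes the week-12 comparison invalid, and the case for change does not rest on precision at week 12. The primary outcome is relapse days and the study is a pilot, so the weight is moderate: worth changing, not a threat to the trial.

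**What to change.** In section 3.2, analyse craving in one baseline-adjusted repeated-measures model with arm-by-visit terms for weeks 4, 8 and 12. Include every randomised participant with at least one post-baseline score. Keep week 12 as the main contrast and report week 8 as a secondary, exploratory contrast, both with confidence intervals. Treat each of the four behaviour association dimensions the same way, and replace the back-reference with the named visits.

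Costs:
- **Effort:** a few sentences in the plan and slightly more analysis. The data are already scheduled, so no visit, questionnaire or participant is added.
- **More contrasts:** five scores (craving plus four dimensions) at two visits give 10 contrasts with about 30 per arm, which is why week 8 should be labelled exploratory.
- **Assumption:** the model relies on data being missing at random. It lets leaving depend on the craving scores already observed, which is weaker than what a completers-only analysis assumes. It may still fail if leaving depends on craving that was never recorded, and the plan should say so.
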